#### Design:

- Demographic data will be collected from the medical record and patient interview for each patient participant. Data will be securely stored in a computerized database.
- Patients will be evaluated by the Urologic Oncology Branch personnel as indicated to rule out or manage other manifestations of VHL. Imaging studies of regions other than the chest and abdomen will be dictated by best clinical practice for the workup and management of VHL manifestations as has been previously published.
- All patients enrolled on this study will be offered genetic counseling by a trained genetic counselor.

Version Date: 08/23/2017

• After their initial on-study evaluation, patients who are not found to have solid lesions of the pancreas but rather have only cystic disease of the pancreas, will be re-screened every two years with non-invasive imaging studies

- Surgical resection of solid lesions of the pancreas will be recommended based on previously published criteria.
- Based on our analysis of likelihood of tumor growth or risk of metastasis, data will be analyzed every two years and appropriate revisions will be made to the surgical management guidelines, if indicated by data analysis.
- Projected accrual will be 25 patients per year for a total of 15 years. Thus, we anticipate accruing 600 patients on this protocol.

*Abbreviated Title:* Pancreatic lesions in VHL *Version Date:* 08/23/2017

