#### 1 INTRODUCTION

#### 1.1 STUDY OBJECTIVES

## 1.1.1 Primary Objectives

- To identify patients with VHL having pancreatic lesions defined by simple cysts, microcystic adenomas, neuroendocrine tumors and other solid lesions of the pancreas.
- To follow patients with VHL and pancreatic manifestations by serial examination with non-invasive imaging studies consisting of CT scan, MRI scan, PET-CT scan, and as clinically indicated, abdominal ultrasound.
- To determine if FDG and FDOPA PET scans can detect early tumor metastasis, and predict which patients will have tumor progression and require an operation based on uptake status. Note: this objective has been met for FDOPA PET imaging. See section 8.
- For patients with solid lesions of the pancreas, to determine the rate of growth and to correlate the growth rate with clinical measures of disease progression such as symptoms.
- To validate non-invasive imaging methods for differentiating benign solid lesions, such as microcystic adenomas, from lesions with malignant potential, namely pancreatic neuroendocrine tumors.
- To characterize the time from initial presentation with pancreatic tumors to the time that surgery is recommended.

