## 1.2 BACKGROUND AND RATIONALE

Patients with von Hippel-Lindau (VHL), a dominantly inherited familial cancer syndrome [1-6], are at risk for developing pancreatic cysts, microcystic adenomas, and pancreatic neuroendocrine tumors (PNETs) [7-9]. PNETs are detected in 12 to 17% of the patients with VHL and these tumors can behave in a malignant fashion, with up to 17% of patients developing metastatic disease [9, 10]. While these neuroendocrine tumors remain a relatively uncommon cause of death, there is a growing recognition of the potential consequences of these tumors if left untreated [6, 9, 10]. We have described previously our experience with the diagnosis and management of these lesions and have made recommendations regarding resection based on size and location of the primary tumor [9]. While this approach appears to have been successful thus far, it has become increasingly evident that some patients manifest a more aggressive phenotype with respect to their pancreatic lesions. Our recommendations for surgery were based on a retrospective review of VHL patients with PNETs who were managed at the NIH. The primary goal of the present protocol is to follow patients diagnosed with PNET in a prospective fashion and to

Version Date: 08/23/2017

apply these management recommendations in order to offer surgery to patients at a time where it may impact on the course of their disease.

Additionally, it has become evident that some patients may manifest a more aggressive phenotype with respect to their pancreatic lesions [11]. Based on this observation, we have previously conducted a retrospective analysis of germ line mutations in patients with VHL and PNETs in order to determine whether or not particular mutations were associated with a more aggressive phenotype [10]. This preliminary study revealed a potential association between mutations in exon 3 and an increased risk of developing metastatic disease. However, given the small number of patients in the study, statistical significance was not reached. Therefore, one of the secondary end points of the present protocol is to conduct germ line mutation analysis in patients found to have PNETs and to correlate differences in germ line mutations with severity of disease.

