## 1.2.1 Surgical resection

Surgical resection of solid lesions of the pancreas will be recommended based on previously published criteria (10). These include:

High suspicion for a PNET with one of the following:

- 1. The solid lesion suspicious for a PNET is  $\geq 2$  cm when located in the head of the pancreas or  $\geq 3$  cm when located in the body or tail of the pancreas.
- 2. A solid lesion of the pancreas, which appears to be growing in size on serial imaging studies.
- 3. Systemic symptoms consistent with a functional neuroendocrine tumor.
- 4. Patients undergoing abdominal operations for other VHL manifestations, such as kidney tumors or adrenal tumors, where extirpation of the pancreatic lesion

Version Date: 08/23/2017

would potentially save the patient an additional surgical procedure in the future

For patients undergoing surgical procedures, tissue will be stored for analysis as outlined in Section 3.4. Since this is a natural history study, our goal will be to enroll as many VHL patients with pancreatic manifestations as is possible.

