## 3.5 OFF STUDY CRITERIA+

- Participant requests to be withdrawn from the study.
- Participant is consistently non-compliant with follow-up appointments.
- Participant is consistently non-compliant with imaging studies.
- Death.
- Loss to follow up.
- PI decision to close the study.
- + Note: Subsequent to the approval of Amendment N, minors are to be retained on the study until they reach the age of majority if possible and can be consented for the future use of their data. If this consent is not obtained, samples and data may not be used in this or future research unless the reason for removal is loss to follow up (for which a waiver has been requested in section 9.6.2) or death (as these samples would no longer fall under human subjects protections).

Version Date: 08/23/2017

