#### 8 STATISTICAL CONSIDERATIONS

We will estimate the distribution of time from initial presentation with pancreatic tumors to the time that surgery is recommended with a Kaplan-Meier Curve. An age-adjusted comparison between this distribution by mutational status (missense vs non-missense mutation, for example) will be done with a proportional hazards model using the method of Wei, et al. (Wei, L.J., Lin, D.Y., and Weissfeld, L., Regression analysis of multivariate incomplete failure time data by modeling marginal distributions. Journal of the American Statistical Association, 84, 1065-1073, 1989) to account for the lack of independence due to familial correlation.

We will estimate the growth rate in solid pancreatic tumors using linear and nonlinear mixed models (Davidian, M. and Giltinan, D.M., Nonlinear Models for Repeated Measurement Data, Chapman and Hall, New York, 1996). These models will allow for the various sources of correlation due to multiple members in the same family and multiple tumors on the same patient. We will compare the growth rate by mutational status as well as by clinical and imaging characteristics by including these factors as covariates in the mixed models. The choice of the form of the linear or non-linear model will depend on the observed data. We will use a linear mixed model on log-transformed volume data if the volume data appears approximately linear on the log-scale. Otherwise, we will investigate alternative models such as the Gompertz model for tumor growth.

The uptake levels of FDG on PET imaging will be compared between patients who require operative intervention and those who do not in order to determine the predictive value of PET imaging in this patient population. Power is based on comparing mean uptake between these two groups of patients. Based on the VHL patient characteristics collected at the Urologic Oncology Branch, NCI, assuming approximately 17% (52 patients) of the targeted 300 VHL patients screened in this study will have solid pancreatic lesion and 50% (26 patients) of them will require operation, we would have 94% power to detect 1 standard deviation difference in the mean uptake between the two groups. The comparison is based on the two-sample t-test at the 5% significance level.

Version Date: 08/23/2017

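### Time to recommended surgery is planned as a Kaplan-Meier curve with no competing event; if deaths are censored, the cumulative probability of a recommendation is modestly overstated

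*Combined protocol and SAP*

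**What the plan says.** Section 1.1.1 (Primary Objectives) includes the aim "To characterize the time from initial presentation with pancreatic tumors to the time that surgery is recommended". Section 8 (Statistical Considerations) is the only place that says how this is analysed. The distribution is to be estimated "to the time that surgery is recommended with a Kaplan-Meier Curve", and then compared by mutational status, adjusted for age, in a "proportional hazards model using the method of Wei, et al", which handles correlation within families.

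Neither section names a competing event, a cumulative incidence function or a censoring rule. Section 3.5 (Off Study Criteria) lists death and "Loss to follow up" side by side as reasons for leaving the study, and nothing separates them for analysis.

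On mortality, section 1.2 says only that "these neuroendocrine tumors remain a relatively uncommon cause of death" and that these tumours can be malignant, "with up to 17% of patients developing metastatic disease". No death rate, from any cause, is given.

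**The concern.** The endpoint is not fatal, so patients can die before reaching it. Someone lost to follow-up may still be recommended surgery later. Someone who has died cannot. The Kaplan-Meier method as usually applied treats both alike: after a censoring it assumes that the patient would have gone on to a recommendation at the same rate as those still observed. Its complement then estimates the probability of a recommendation in a setting where nobody dies first, and it exceeds the proportion of real patients who reach one.

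The low mortality from the pancreatic tumours themselves does not settle the matter, because death from any cause competes. VHL affects several organs, and sections 1.2.1 and 3.1.2 refer to kidney and adrenal tumours and to neurosurgical and neuro-oncology evaluation. At stake is the absolute probability reported for a primary objective of a natural history study.

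**Working it through.** **No figure to reproduce.** The documents attach no event count, probability, power or sample size to this curve. The check therefore covers the direction of the bias and its plausible range.

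**Direction.** At each recommendation time, let d be the number of recommendations and n the number at risk.

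- Aalen-Johansen adds up S(t−) × d/n, where S is the probability of being alive and without a recommendation.
- One minus Kaplan-Meier, with deaths censored, adds up K(t−) × d/n, where K ignores deaths.
- S is never above K, so one minus Kaplan-Meier is never below the cumulative incidence. It is above it as soon as a death precedes a later recommendation.

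**Size: inputs.**

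- F1, the true cumulative incidence of recommended surgery: 24/129 = 18.6%, from section 8 (129 patients with solid lesions by April 2014, 24 of whom required an operation). This is a proxy. It counts operations rather than recommendations, and it is a crude proportion over unequal follow-up.
- F2, the proportion dying before a recommendation: assumed to be 2, 5, 10 or 20%, since the documents give no value.
- Constant cause-specific hazards: assumed.

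**Formula.** The total cumulative hazard is H = −ln(1 − F1 − F2). The share belonging to recommendation is F1/(F1 + F2). Hence

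1 − KM = 1 − exp(−H × F1/(F1 + F2)) = 1 − (1 − F1 − F2)^(F1/(F1 + F2)).

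Worked case, F2 = 10%: H = −ln(0.71395) = 0.3369; share = 0.18605/0.28605 = 0.6504; product = 0.2191; 1 − exp(−0.2191) = 19.68%.

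| Die first (assumed) | 1 − KM if true incidence is 18.6% | Overstatement (points) | 1 − KM if true incidence is 50% (assumed) | Overstatement (points) |
|---|---|---|---|---|
| 2% | 18.81% | 0.20 | 50.63% | 0.63 |
| 5% | 19.12% | 0.52 | 51.61% | 1.61 |
| 10% | 19.68% | 1.07 | 53.40% | 3.40 |
| 20% | 20.95% | 2.35 | 57.68% | 7.68 |

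**Growth with follow-up.** With hazards h for recommendation and d for death, the incidence at T years is h/(h + d) × (1 − exp(−(h + d)T)), against 1 − exp(−hT) from Kaplan-Meier. At assumed annual hazards of h = 5% and d = 1%:

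- 5 years: 21.6% against 22.1%, a gap of 0.5 points.
- 10 years: 37.6% against 39.3%, a gap of 1.7 points.
- 15 years: 49.5% against 52.8%, a gap of 3.3 points.

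**Scale against sampling error.** The simple binomial 95% half-width for 24/129 is 1.96 × √(0.186 × 0.814/129) = 6.7 points.

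**Resection during another operation.** Section 1.2.1 lists, among the grounds for recommending resection of a suspected PNET, "Patients undergoing abdominal operations for other VHL manifestations, such as kidney tumors or adrenal tumors" where removing the pancreatic lesion could spare a later procedure. Section 3.3.2 sets out grounds for surgery on solid lesions and omits this one. Under section 1.2.1 such a case is the event of interest; under section 3.3.2 its status is unclear. Neither section makes it a competing event.

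**The case against.** The strongest reply has three parts.

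First, the plan never says that deaths are censored. That is correct: it is an inference from the usual use of the method and from the absence of any other rule. The conclusion is conditional on it.

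Second, the effect is probably small. At the only proportion the documents supply, even 20% dying first gives a bias well inside the 6.7-point half-width, and the 20% figure has no basis in the documents. This stands as a limit on importance. It does not remove the point, because the bias always runs one way and more patients do not reduce it.

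Third, a net probability, supposing that nobody dies, can be a legitimate target. It can, but the plan does not say it wants one, and the stated aim of describing when surgery is recommended in a natural history study reads more naturally as what happens to actual patients.

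Some stronger readings are tempting and should be resisted:

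- A reader might count removal of the lesion during another abdominal operation as a second competing event. Section 1.2.1 makes it a ground for recommending resection, so that coding would turn events into non-events and pull the estimate down.
- A reader might infer 15 years of follow-up from "Projected accrual will be 25 patients per year for a total of 15 years". That is the accrual period. Long follow-up is possible for early entrants, but no length is stated.
- A reader might suppose that the curve drives patient counselling or the two-yearly review of surgical guidance. The counselling described is genetic, and sections 8 and Design tie the review to tumour growth and metastasis risk, not to this curve.

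**Conclusion.** The point holds as a minor, conditional one. If deaths before a recommendation are censored, the curve overstates the cumulative probability of recommended surgery: by about 0.20 to 2.35 points for 2 to 20% dying first at an incidence of 18.6%, and by more at higher incidence or with longer follow-up. These sizes rest on an assumed death rate, constant hazards and a proxy for the incidence; only the direction is free of those assumptions.

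The comparison by mutational status is not undermined. It can be read as a comparison of cause-specific hazards. It would be wrong to infer that the study's power or precision calculations are affected: those in section 8 concern PET uptake, the PET detection proportion and growth rates, and none uses this curve.

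**What to change.** In section 8:

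1. Report the cumulative incidence of recommended surgery by the Aalen-Johansen estimator, with death from any cause before recommendation as the competing event.
2. State that only loss to follow-up, withdrawal and end of observation are censored.
3. Describe the proportional hazards model as a model for the cause-specific hazard of recommendation, keeping the planned handling of family correlation.
4. Reconcile sections 1.2.1 and 3.3.2 on resection during another abdominal operation, and have the endpoint definition count such cases accordingly. Do not code them as competing events.

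The cost is a few sentences and a standard routine, and the headline proportion will be slightly lower. Dates of death and of recommendation must both be available. Deaths are known through the off-study notification (sections 3.5 and 3.5.1) and the reporting of Grade 5 events (section 7.2.2). The case report form list in section 6.2.1 mentions neither date, so the sponsor should confirm that both are recorded.

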## 3.1.3 Non-invasive imaging

- CT scan with contrast of the chest, abdomen, and pelvis
- MRI of the abdomen with special attention to the pancreas as indicated
- Abdominal ultrasound exam as indicated by the CT and MRI scans to further evaluate cystic lesions.
- FDG PET scans for pancreatic lesions that are solid on CT scan or MRI.

**NOTE:** Due to the amount of radiation exposure, PET imaging will NOT be performed on children under the age of 18 or pregnant or nursing women.

Bi-dimensional tumor measurements will be performed on contrast CT scans to evaluate rate of tumor growth and tumor doubling, on scans obtained at baseline and at each follow up visit.

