#### 3.3 SURGICAL MANAGEMENT

Surgery will be recommended to manage lesions within the pancreas under the following circumstances:

Version Date: 08/23/2017

3.3.1 Patients with cystic disease who develop symptoms attributable to their cysts consisting of pain, early satiety or intestinal obstruction will undergo appropriate management of their cysts by best clinical practice (this may include cystectomy, cyst drainage, or internal bypass).

- 3.3.2 Patients with solid lesions of the pancreas that are thought to be PNETs by non-invasive imaging studies will be considered for surgery if:
  - Their solid lesion is enlarging on serial imaging studies.
  - Their solid lesion is associated with symptoms consistent with a pancreatic neuroendocrine tumor.
  - A solid lesion in the head of the pancreas is  $\geq 2$  cm in size.
  - A solid lesion in the body or tail of the pancreas is  $\geq 3$  cm in size.
- 3.3.3 Patients who present with evidence of a pheochromocytoma or other cardiac risk factors will undergo a cardiac evaluation prior to surgical intervention.
- 3.3.4 Patients will be offered surgical management if they meet one of these criteria and the type of operation will be dictated by best clinical management taking into account the desire to preserve as much normal pancreatic tissue as possible. Approaches to the management of solid lesions of the pancreas can range from simple enucleation to distal pancreatectomy and splenectomy or a pancreatico-duodenectomy. Whenever possible, lesions in the pancreas will be managed by a laparoscopic approach. In all cases, intraoperative ultrasound will be utilized during surgical procedures in order to identify and manage additional lesions, as well as to minimize the risk of injury to vessels or the pancreatic duct.

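### The operated v non-operated comparison of FDG uptake is not adjusted for CT size, location or growth, which partly decide who is operated on, so it cannot show that uptake adds to CT

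*Combined protocol and SAP*

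**What the plan says.** One primary objective (Section 1.1.1) is to learn whether FDG PET can "predict which patients will have tumor progression and require an operation based on uptake status".

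Section 8 answers it with a comparison of group means: "The uptake levels of FDG on PET imaging will be compared between patients who require operative intervention and those who do not", and this is done "in order to determine the predictive value of PET imaging in this patient population". On method it adds only: "The comparison is based on the two-sample t-test at the 5% significance level". The power statement works from this premise: "assuming approximately 17% (52 patients) of the targeted 300 VHL patients screened in this study will have solid pancreatic lesion". It then splits that group evenly ("and 50% (26 patients) of them will require operation") and arrives at 94% power for a difference of 1 SD.

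Sections 1.2.1 and 3.3.2 say what leads to operation. The criteria include a size of at least 2 cm in the head of the pancreas, and "A solid lesion in the body or tail of the pancreas is" at least 3 cm. Enlargement on serial imaging and symptoms are also listed, and Section 1.2.1 adds abdominal surgery for another VHL manifestation. Section 3.2.2 describes the patients under yearly surveillance as those whose lesions are still below the size criteria.

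No covariate, stratification or matching is named for the uptake comparison. Elsewhere Section 8 does name covariates: age in the time-to-surgery model, and clinical and imaging characteristics in the growth models.

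The data needed for adjustment are collected. Section 3.1.3 states: "Bi-dimensional tumor measurements will be performed on contrast CT scans to evaluate rate of tumor growth and tumor doubling", at baseline and each follow-up visit, and Section 6.1 repeats this.

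**The concern.** The two groups are separated in part by what the CT shows: how large the lesion is, where it lies and whether it is growing. If uptake also varies with size, the operated group will have a different mean uptake for that reason alone. The t-test cannot tell this apart from uptake that carries information of its own. Complete follow-up and a fixed index scan would not remove the problem.

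What is at stake is how a positive result is interpreted. The CT measurement is already used to decide on operation, so a PET result is useful to the extent that it adds to CT. The planned test does not address that question, and a significant result could be taken as if it did.

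**Working it through.** **Step 1. Reproduce the plan's figure.** Inputs from Section 8: 26 v 26 patients, a 1 SD difference, 5% level. Noncentrality = 1/√(1/26 + 1/26) = √13 = 3.61 with 50 df. The two-sided t-test has 94.2% power, which agrees with the stated 94%. (One-sided it would be 97.2%.) The power figure is not at fault.

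**Step 2. What size alone can produce.** Assumptions, because the documents give neither value:
- r is the within-group correlation of uptake with lesion size, 0 to 0.7.
- d is the mean size gap between operated and non-operated patients in within-group SDs, 0.5 to 2.
- Given size, uptake does not differ between the groups.

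The expected difference in mean uptake is then r × d SD. The rejection rate is the noncentral-t probability at that difference, two-sided 5%. The last column uses the counts that Section 8 reports for April 2014: 129 patients with solid lesions, 24 operated, so 129 − 24 = 105 not operated.

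| r | d | r × d (SD) | Rejects, 26 v 26 | Rejects, 24 v 105 |
|---|---|---|---|---|
| 0 | any | 0 | 5% | 5% |
| 0.2 | 0.5 | 0.10 | 6% | 7% |
| 0.3 | 1 | 0.30 | 19% | 26% |
| 0.5 | 1 | 0.50 | 42% | 59% |
| 0.5 | 1.5 | 0.75 | 76% | 91% |
| 0.5 | 2 | 1.00 | 94% | 99% |
| 0.7 | 1.5 | 1.05 | 96% | over 99% |

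At r = 0.5 and d = 2, size alone produces the whole 1 SD difference that the plan is powered to detect.

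**Step 3. The same data with size in the model.** In simulation (2,000 runs per cell), a linear model of uptake on operation group plus size rejected for group in about 4% to 6% of runs in every cell.

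**Step 4. What adjustment costs.** With equal groups, the share of the variance of size explained by group is R² = 0.25d²/(1 + 0.25d²). For a group difference of 1 residual SD at given size, noncentrality = √(52 × 0.25 × (1 − R²)) with 52 − 3 = 49 df. Example, d = 1: R² = 0.25/1.25 = 0.20, noncentrality = √10.4 = 3.22, power 88.5%.

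| d | R² | Power, 52 patients | Patients for 94% |
|---|---|---|---|
| 0.5 | 0.06 | 92.9% | 56 |
| 1 | 0.20 | 88.5% | 64 |
| 1.5 | 0.36 | 80.7% | 80 |
| 2 | 0.50 | 70.5% | 102 |

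These figures hold for 1 SD at given size. If instead 1 SD is the raw difference and part of it is due to size, less is left. At r = 0.5 and d = 1 the adjusted effect is (1 − 0.5)/√(1 − 0.25) = 0.58 residual SD, and power is about 45%.

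**The case against.** The strongest reply is that the t-test does what it says. Its null hypothesis is equal mean uptake. If operated patients truly have higher uptake, for whatever reason, rejecting is correct. The protocol speaks of prediction and predictive value, not of value beyond CT, and marginal prediction needs no adjustment. This stands. A reader might take the percentages above for false-positive rates of the planned test, or conclude that the test is invalid. Neither follows: they are errors only for a claim that uptake adds to CT.

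A reader might also take it as established that uptake rises with size. The documents report no such relation, and at r = 0 the excess disappears. The size gap is equally unknown. Symptoms and concurrent surgery also lead to operation and may narrow it. Follow-up PET is listed for lesions below the size criteria, which would narrow it at those scans, although baseline PET has no size limit.

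A reader might further infer that a PET effect due only to size would pass into the surgical guidelines. Section 8 ties their two-yearly revision to the likelihood of growth and the risk of metastasis. It does not name this comparison, so the link is possible but not stated.

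Finally, Section 8 does compare PET with CT directly, through the proportion of surgical patients in whom FDG PET showed metastasis that CT missed, or non-neoplastic disease. That analysis underlies the current target of 600 screened patients, so the value of PET does not rest on the t-test alone. But it concerns detection. It does not say whether the level of uptake predicts operation once CT size is known.

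**Conclusion.** The point holds as a limit on what the planned comparison can show. As written, it cannot separate uptake from the CT findings that help define the outcome. If uptake carries nothing beyond size, the 26 v 26 test still rejects in anything from 5% to over 95% of studies across the assumed ranges, with 42% at r = 0.5 and d = 1. The existence of the gap rests on the text alone: no covariate is named, and size, location and enlargement are operation criteria. Its magnitude rests entirely on r and d, which the documents do not give, so the percentages are illustrations and not estimates for this cohort. The plan should be changed on this point, and the data for it are already collected.

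**What to change.** In Section 8:
- Keep the t-test as the descriptive, marginal comparison.
- Add an analysis of uptake adjusted for CT size at the time of that PET, for location (head v body/tail) and, where an earlier CT exists, for prior growth. Growth belongs there because enlargement is itself a criterion for operation.
- Pre-specify one index lesion per patient. Section 8 reports 98 lesions in 40 patients, so a patient's lesion size is otherwise undefined.
- Use either a linear model of uptake on operation group plus these covariates, or a penalised logistic model of operation. Size and location may nearly determine operation, and ordinary logistic regression could then fail through separation.
- State that predictive value beyond CT will be claimed only from the adjusted effect.
- Restate power for that effect: about 93%, 88%, 81% and 71% at 52 patients for size gaps of 0.5, 1, 1.5 and 2 SD, recalculated on the actual number of adults with PET.

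No new measurements are needed. The cost is the lower power. The 129 patients with solid lesions seen by April 2014 exceed the 56 to 102 needed for 94% with equal groups. However, the split of 24 v 105 is unequal and PET is limited to adults, so that count cannot be assumed to restore the stated power.

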Recent studies suggest that functional imaging with FDG and FDOPA-PET scans is helpful for localizing and for possibly distinguishing malignant from benign neuroendocrine pancreatic lesions [12, 13]. Therefore, we will include functional imaging of solid pancreatic lesions in the adult population to determine if an uptake threshold could be used to distinguish malignant from benign solid pancreatic lesions.

The FDG and FDOPA PET scans will be used in adult patients found to have a solid pancreatic lesion. In this cohort of patients, the use of FDG and FDOPA-PET scans may help detect early tumor metastasis, and predict which patients will have tumor progression and require an operation based on uptake status. Review of the imaging studies of this cohort of patients revealed that only 11 of the 98 lesions (11%) were positive on F-DOPA as compared to CT scan. Based on this interim analysis, F-DOPA did not seem likely to be useful for detecting pancreatic neuroendocrine tumors in patients with VHL and with amendment H was eliminated from this protocol.

PET-MRI imaging was recently approved for clinical use and may be more accurate for localizing pancreatic tumors, in general [14]. Therefore, we will include PET-MRI imaging of solid pancreatic lesions in the adult population to determine if this modality could be used to detect pancreatic neuroendocrine tumors, predict growth, and distinguish between benign and malignant PNETs.

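### Section 8 analyses FDG uptake levels only by comparing means between patients who do and do not need an operation, which yields no cut-off or predictive value

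*Combined protocol and SAP*

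**What the plan says.** Three places in the combined protocol and SAP bear on this.

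- **Section 1.1.1 (primary objectives).** FDG PET is to show whether it can detect early metastasis and "predict which patients will have tumor progression and require an operation based on uptake status". The note there says the objective has been met for FDOPA, so it remains open for FDG. A separate primary objective is "To validate non-invasive imaging methods for differentiating benign solid lesions, such as microcystic adenomas, from lesions with malignant potential".
- **Section 1.2 (rationale).** Functional imaging of solid lesions in adults is included "to determine if an uptake threshold could be used to distinguish malignant from benign solid pancreatic lesions".
- **Section 8.** Uptake levels "will be compared between patients who require operative intervention and those who do not in order to determine the predictive value of PET imaging". The section continues: "Power is based on comparing mean uptake between these two groups of patients". As design inputs it takes 300 screened patients and expects 52 of these, given as 17%, to have a solid lesion. The power statement for those 52 reads: "50% (26 patients) of them will require operation, we would have 94% power to detect 1 standard deviation difference in the mean uptake". On the test, it says: "The comparison is based on the two-sample t-test at the 5% significance level".

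Section 8 uses FDG-PET in one other way. Among 24 surgical patients it counts 3 with metastasis not seen on CT and 4 with non-neoplastic disease, 7/24 = 29%, with a 90% interval of 16.5% to 46%. It also allows imaging characteristics as covariates in the tumour growth models.

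**The concern.** The aims are about prediction and classification: given a patient's uptake, how likely is an operation, and is there a value that separates malignant from benign lesions? The planned statistic answers a different question, whether average uptake differs between two groups. Nowhere does the document plan a cut-off rule, an ROC curve or AUC, sensitivity, specificity, PPV or NPV for uptake, or validation of a threshold.

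The grouping raises a second difficulty. Under Section 3.3.2 patients are considered for operation on growth, symptoms, or size and location, so having an operation is not the same as having a malignant lesion. Section 8 itself counts 4 patients with non-neoplastic disease in its surgical yield.

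At stake is how a significant t-test would be read. Because Section 8 calls the comparison a determination of predictive value, a small p-value could be reported as showing that PET predicts operation, even where it says little about an individual patient. Section 8 also provides for analyses every two years that may lead to revised surgical management guidelines.

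**Working it through.** **Step 1. Reproduce the plan's figure.** Inputs from Section 8: 26 v 26, a 1 SD difference, 5% level. The sentence does not state sidedness; two-sided is assumed. With 50 degrees of freedom and noncentrality 1/√(1/26 + 1/26) = 3.61, the noncentral t distribution gives power 94.2%, which matches the stated 94%. A one-sided test would give 97.2%, which does not match. With the counts observed to April 2014 (24 operated, 129 − 24 = 105 not), power at 1 SD is about 99%. Power for the mean comparison is therefore not the problem.

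**Step 2. Assumptions for the illustration.** The documents give no uptake distribution. Assume normal uptake with equal SDs, a difference of d SDs and a cut-off midway between the means. Then:
- AUC = Φ(d/√2)
- sensitivity = specificity = Φ(d/2)
- PPV and NPV follow from Bayes' rule at the operated share p = 24/129 = 18.6%.

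**Step 3. The difference the plan is powered for (d = 1).**
- AUC = Φ(0.707) = 0.76
- Sensitivity = specificity = Φ(0.5) = 0.691
- PPV = 0.691 × 0.186 / (0.691 × 0.186 + 0.309 × 0.814) = 34%
- NPV = 0.691 × 0.814 / (0.691 × 0.814 + 0.309 × 0.186) = 91%

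At the planned 50% operation rate the same difference gives PPV = NPV = 69%. One mean difference is thus compatible with a PPV of 34% or 69%, depending only on the share operated.

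**Step 4. The smallest observed difference that reaches significance.** Critical d = t(0.975) × √(1/n₁ + 1/n₂). The last row projects current counts to 600 screened: 600 × 129/276 ≈ 280 with solid lesions, of whom 600 × 24/276 ≈ 52 operated and 228 not.

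| Groups | Critical d | AUC | PPV at 18.6% |
|---|---|---|---|
| 26 v 26 | 0.56 | 0.65 | 26% |
| 24 v 105 | 0.45 | 0.62 | 25% |
| 52 v 228 | 0.30 | 0.585 | 22.5% |

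As the sample grows, significance is reached at differences that carry less information about an individual. In the last row PPV is 22.5% against a base rate of 18.6%.

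**Step 5. A cut-off needs its own plan.** In a simulation under the same model (26 v 26, d = 1), the cut-off maximising Youden's index ranged from about −0.4 to 1.3 SD above the non-operated mean (95% range). Its apparent index was too high by about 0.12 on average. A threshold picked from the data without correction would be unstable and optimistic.

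**Step 6. Can discrimination be estimated?** At AUC 0.76 the Hanley–McNeil standard error is about 0.06 for 24 v 105 and 0.04 for 52 v 228. These are best cases: the counts are of all patients with solid lesions, and Sections 3.1.3 and 3.2.2 exclude patients under 18 and pregnant or nursing women from PET. The number with FDG uptake values is not given.

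**The case against.** Several points on the other side stand and limit what can be said.

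- **The threshold is rationale.** A reader might infer that a malignant-versus-benign uptake cut-off is a listed objective. It appears only in Section 1.2. The primary objective asks for prediction of progression and operation, so the operation grouping does match part of it. The separate objective on benign versus malignant potential concerns imaging generally and names no uptake threshold. Even so, uptake status implies a cut-off, and none is defined.
- **There is other FDG work in Section 8.** It would be wrong to infer that the mean comparison is the only FDG analysis. The 7/24 yield addresses metastasis detection and drives the 600-patient target, and the growth-model covariates may bear on progression. Neither gives an uptake cut-off or its accuracy.
- **Other summaries are not forbidden.** Section 8 first speaks of comparing uptake levels, and the t-test sentence belongs to the power paragraph. The fair charge is that nothing beyond the mean comparison is specified.
- **The illustration does not show that FDG-PET is useless.** At the planned 1 SD the AUC is 0.76, and the midpoint NPV is 91% against 81% with no test. A cut-off 1.5 SD above the non-operated mean would give sensitivity 31%, specificity 93% and PPV about 51%. The weak values belong to results that only just reach significance.

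Means and SDs could be converted to an AUC under normality, but the plan includes no such step or assumption.

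**Conclusion.** The point holds for the analysis of FDG uptake levels. Followed as written, Section 8 would establish whether mean uptake differs by operation status. It would not provide prediction from uptake status, and its grouping cannot answer the threshold question posed in the rationale.

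The AUC, PPV and NPV figures are illustrations. They rest on assumed normality, equal SDs, a midpoint cut-off, the 24/129 operated share and, for 52 v 228, a projection from 2014 counts. That a mean difference does not itself supply a cut-off or a predictive value depends on none of these. The 94% power is right, and nothing here implies a sample-size error. The change should be made; the scans and the power calculation for the mean comparison are unaffected.

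**What to change.** Amend Section 8 as follows.

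1. For need for operation, make the FDG uptake summary an AUC with 95% CI. Use a time-dependent form, because follow-up varies and time to operation is censored.
2. Report sensitivity, specificity, PPV and NPV at a cut-off chosen by a pre-specified rule, with bootstrap or cross-validation correction for optimism.
3. Use intervals that allow for clustering by patient (several lesions) and by family, as Section 8 already does for growth.
4. Keep the mean difference as descriptive.
5. Report malignant (histology or metastasis) versus not malignant separately and as exploratory. State that histology will come mainly from operated patients, so verification bias is likely, and that the interval will be wide.
6. State how many patients have FDG uptake values.

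The cost is revised wording in Section 8 and modest extra analysis on data already being collected. The downside is wide intervals, especially for malignancy, where confirmed cases may be few.
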